2.5 Measures

Primary Outcome Measures

The Primary Outcome measures for this study include one to measure stigma and three to measure acceptability, appropriateness and feasibility of the pilot stigma reduction training intervention.

To measure stigma, we will use a modified Opening Minds Scale for Health Providers (OMS-HC) which is an 8-item scale measuring stigma amongst health workers toward people who use drugs. Each item consists of a 5-point Likert scale, with 5 indicating the highest degree of agreement with the statement. The score is calculated additively with a range of 8-40. Higher scores indicate a higher level of stigma. Included items are:

- If I were under treatment for drug addiction, I would not disclose this to any of my colleagues.
- If I had drug addiction, I would seek treatment at a health facility away from the one I work in.
- I would see myself as weak if I had drug addiction and could not fix it myself
- I would be reluctant to seek help if I had drug addiction
- Despite my professional beliefs, I have negative reactions towards people who use drugs
- I would not want a person with addiction, even if it were managed, to work with children.
- Healthcare providers do not need to be advocates for people who use drugs.
- I am afraid to provide health services to people who use drugs

We will measure implementation outcomes at endline by assessing feasibility, acceptability and appropriateness of the intervention. Each measure has 4 items. They are measured in a five Likert scale including the following responses with scale values ranging from 1 to 5: completely disagree (1), disagree (2), neither agree nor disagree (3), agree (4), and completely agree (5). No items need to be reverse coded. Higher scores indicate greater acceptability, appropriateness, or feasibility.

Secondary Outcome Measures

We will include two secondary outcome measures:

1) A modified *Drug and Drug Problems Perceptions Questionnaire* to capture self-assessed and self-reported knowledge about drug use and how to provide services to people who use drugs. The measure uses a Likert scale (1-5) and has 8 (for non-clinical staff) and 10 (for clinical staff) items. Clinical staff receive 2 additional items. Scores (range:1-5) and are calculated by taking the mean value of responses to all questions. Higher scores correspond to higher degrees of knowledge and therefore a better outcome.

Items include the following:

I feel

- I have a working knowledge of drugs and drug related problems.
- safe providing HIV services to people who use drugs (PWUD)

I feel I know enough about {insert below item} to carry out my role providing HIV services to PWUD

- the causes of drug problems
- the physical effects of drug use
- the psychological effects of drugs
- the factors which put people at risk of developing drug problems

I feel I know enough about {insert below item} to provide appropriate services to PWUD

- drug addiction as a brain disease
- the social effects of drug use
- drug-to drug interactions (CS only)
- co-occurring conditions (CS only)

2) A modified *Bogardus Social Distance Scale*

This is a 6-item scale measuring social distance, or (un)willingness to interact with a person who uses drugs in different social interactions. The response options are on a 4-point Likert scale, with 4 indicating a response of "definitely yes" and 1 indicating "definitely no". The score is calculated additively with a range of 6-24. Higher scores correspond to higher degrees of social distance and therefore a worse outcome.

Included items:

- Would you feel ashamed if people knew someone in your family has drug addiction?
- Would you be afraid to have a conversation with someone who uses drugs?
- Would you be disturbed about working at the same health facility with someone who uses drugs?
- Would you stop being friends with someone who uses drugs?
- Would you feel upset or disturbed being in the same room with someone who uses drugs?
- Would you marry someone who uses drugs? (reverse coded)

Other measures

Marlowe-Crowne Social Desirability Scale (MCSDS)

Due to the sensitive nature of the topic, social desirability bias in responses at endline of the intervention is a possibility. We therefore will include the MCSDS, which has been adapted and validated in East Africa, to control for this possibility.

Level of contact report

A 5-item scale that measures the amount that a respondent comes into contact with people who use drugs in professional, social, and personal situations. Each item consists of a dichotomous true/false response, with true indicating that the person agrees with the statement. Scores are calculated dichotomously: agreement with none of the 5 items indicates a low degree of contact ("low contact"), and agreement with one or more of the 5 items indicates a high degree of contact ("high contact").

Sociodemographic characteristics

These include sex, age, and education. Other characteristics which will be assessed will include position of a health worker in CTC (clinical vs non-clinical staff), length of service in health care, length of service in CTC, and frequency of contact in the CTC with clients who use drugs.

Participation in stigma reduction training

Participants will be asked to self-report if they have ever had training on stigma and discrimination reduction (baseline) and then at endline more detailed questions will be asked about participation in the pilot study intervention.

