2. To evaluate the acceptability, appropriateness, and feasibility of the adapted drug use stigma-reduction intervention.

Methods

Study design and procedures: Guided by the ADAPT-ITT model, which provides a framework and prescriptive method for adapting evidence-based interventions (EBIs), we will employ a mixed methods design to adapt, and pilot test the intervention, including pre-post surveys with CTC staff and post intervention focus group discussions. A formative (qualitative) phase of research will be conducted with PWUD and clinical and non-clinical CTC staff to inform the first step in the adaption of the HIV stigma-reduction intervention to focus on drug-use stigma. We will pilot the adapted participatory training intervention for health care staff in seven high-volume HIV clinics in areas with the highest concentration of PWUD in Dar-es-Salaam, the Ilala, Kinondoni, and Temeke Municipal Councils.

Measurements: The key outcome measures will be three scales to measure stigma and a self-assessed and reported measure of knowledge of drug use. In addition, we propose to collect socio-demographic characteristics, a measure of social desirability bias, and level of contact with PWUD. The implementation outcome measures will be feasibility, acceptability, and appropriateness of the intervention.

Data analysis: Qualitative data will be analyzed using a multi-stage, modified grounded theory approach. To confirm the validity of the scales we will conduct confirmatory factor analyses (CFA) on the scales we do not modify and exploratory factor analyses (EFA) on those that we do. To examine the intervention effect, we will fit linear mixed effect regression models using the R package lme4 to examine changes in outcome measures from pre- to post-intervention while controlling for repeated measurements via random intercepts by individual. Each model will control for type of clinic, type of staff (clinical vs. non-clinical), gender, age, years of service in health facilities, years of service in an HIV

clinic, social desirability, level of contact with PWUD, and number of clients who use drugs treated within the last month. In addition, to identify possible effect modifiers (e.g., staff type, gender, level of contact with drug users), we will test time by modifier interaction terms within these models.

1. Introduction

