We will calculate descriptive statistics for all collected variables: counts and percentages for categorical variables, means and standard deviations for continuous variables. We will also calculate participants' scale responses using additive or averaging methods as recommended by the literature. To examine the changes in our outcome variables between the pre-intervention and post-intervention surveys, we will fit linear mixed effect regression models using the R package *lme4* with each outcome variable as our dependent variable and time (pre- vs. post-intervention) as our primary independent variable. In these linear mixed effect regression analyses, we will control for repeated measures by individuals by including random intercepts by individual respondent; all other parameters will be included as fixed effects. We will use the function *lme4::confint* to generate bootstrapped 95% confidence intervals with 1,000 replicates. To assess model fit, we will use likelihood ratio tests (alpha = 0.05). We will visually inspect residual plots for homoscedasticity and normality.

In addition to univariate regression analyses for each of our outcomes of interest, we will conduct regression analyses that control for clinic, type of staff, gender, age, years of service in health facilities, years of service at an HIV health clinic, number of clients who use drugs treated within the last month, and social desirability bias. In addition, we will individually test each control parameter for an interaction with time, which would indicate a differential change in the outcome of interest over time by the parameter in question.

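### The time-by-staff-type test on the knowledge score compares a 10-item mean with an 8-item mean, so it picks up item content as well as any differential change

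*Protocol*

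**What the plan says.** Protocol 2.5 (Secondary Outcome Measures) defines the knowledge measure as a modified questionnaire with 1-5 responses that "has 8 (for non-clinical staff) and 10 (for clinical staff) items". The scoring rule is "Scores (range:1-5) and are calculated by taking the mean value of responses to all questions". The item list marks the two clinical-only items: "drug-to drug interactions (CS only") and "co-occurring conditions (CS only").

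The SAP (Statistical Analysis) fits a linear mixed model to each outcome with time as the main predictor and a random intercept per respondent. The adjusted models "control for clinic, type of staff, gender, age" and further covariates. It adds that "we will individually test each control parameter for an interaction with time", which includes staff type by time on the knowledge score. The Protocol abstract likewise plans interaction tests for "possible effect modifiers (e.g., staff type, gender, level of contact with drug users").

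The SAP's only scoring text is a general reference to additive or averaging methods from the literature. Neither document says that pooled or interaction models use only the items asked of everyone.

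**The concern.** The item set is determined entirely by staff type, and staff type is the modifier being tested. No covariate can separate the two. A significant interaction could mean that clinical and non-clinical staff responded differently to the training. It could also mean only that the two clinical-only topics moved more, or less, than the other eight. The same term can hide a real difference.

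The documents give some reason to expect unequal movement. Protocol 1.2 mentions new material on drug use as a medical condition, which bears on shared items such as addiction as a brain disease. It describes no content on drug interactions. On the other hand, a provider of medication-assisted treatment and an addiction specialist help deliver the training. The direction of any gap is therefore unknown.

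What is at stake is whether a pilot finding that the training works better for one staff group can be taken at face value when a later trial is designed.

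**Working it through.** **Item count.** The Protocol list has 2 items under the first stem, 4 under the second, and 4 under the third, of which 2 are clinical-only. That gives 2 + 4 + 2 = 8 shared items and 8 + 2 = 10 for clinical staff, which matches the stated counts. A mean of 1-5 responses has range 1-5 in both groups, also as stated.

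**Inputs from the documents.** Item counts and scoring rule (Protocol 2.5); 131 people with both measurements and significance level 0.05 (Protocol 2.4 and SAP Power Analysis).

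**Assumed inputs, not in the documents.** Two-sided test; SD of change in the score 0.6 to 0.8; even staff split (65.5 per group); gap between the change in extra items and the change in shared items of 0, 0.25 or 0.5 points. A wider range is given below.

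**Algebra.** Let C8 and N8 be the mean change on the eight shared items in clinical and non-clinical staff, and C2 the mean change on the two extra items.

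- Clinical change in score = (8 x C8 + 2 x C2)/10 = 0.8 x C8 + 0.2 x C2
- Non-clinical change in score = N8
- Interaction = (C8 - N8) + 0.2 x (C2 - C8)

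The first term is the difference on common content. The second is the artefact. If C8 = N8, only the artefact is left.

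**Examples with C8 = N8 = 0.5.**

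- C2 = 0: clinical change 0.40, artefact 0.2 x (0 - 0.5) = -0.10
- C2 = 0.5: clinical change 0.50, artefact 0
- C2 = 1.0: clinical change 0.60, artefact +0.10

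Masking works the same way. If C8 - N8 = 0.1 and C2 - C8 = -0.5, the interaction is 0.1 - 0.1 = 0.

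**False-positive rate.** For complete pairs, the unadjusted interaction is the difference in mean change, with SE = SD x sqrt(1/65.5 + 1/65.5). The rejection rate is P(Z > 1.96 - artefact/SE) + P(Z < -1.96 - artefact/SE).

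| Gap | Artefact | SD 0.6 (SE 0.105) | SD 0.8 (SE 0.140) |
|---|---|---|---|
| 0 | 0 | 5% | 5% |
| 0.25 | 0.05 | 7.6% | 6.5% |
| 0.5 | 0.10 | 15.9% | 11.0% |

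Over a clinical share of 40-70% and an SD of change of 0.6-1.0, the rate is about 6-8% at a gap of 0.25, 8-16% at 0.5, and 18-48% at 1.0.

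**Simulation check.** There were 4,000 replicates with 66 clinical and 65 non-clinical staff, SD of each item's change 1, and correlation 0.5 between item changes. At a gap of 0.5 in either direction, the stated scoring rejected in 11.8% and 11.9% of runs. With both groups scored on the eight shared items, rejection was 4.6% to 5.5% in all settings, whatever the extra items did.

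**The case against.** The strongest defence is that the score is meant to be role-specific. The stems ask whether staff know enough for their own role and services, and the two extra topics belong to the clinical role. A different change on them is then a real difference in the defined outcome, and averaging already removes the effect of questionnaire length. This stands as a case for the 10-item mean as a description of clinical staff. It does not justify comparing the two groups on it, because a reader of a staff-type interaction will take it as a different response to the same training on the same content.

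It is also fair that the size rests wholly on assumed changes and SDs, that the bias vanishes if the extra items move with the others, and that this is one of many exploratory interactions.

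A reader might infer more than the documents support in three ways:

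- *That the two groups complete different instruments.* All eight non-clinical items are in the clinical version, so shared items carry 8/10 = 80% of the clinical score. The extra items use the same response scale and share a stem with two of the common items.
- *That the main knowledge result is compromised.* The main predictor is time, within person. If each respondent gets the same version at both rounds, that change is like-for-like. A constant level difference due to the item set is absorbed by the staff-type covariate in the adjusted model.
- *That the factor analysis is flawed.* The SAP introduces knowledge as a section of the survey, apart from the three scales, and its factor-analysis text refers to the scales. Because the Protocol calls the questionnaire modified, an exploratory factor analysis is possible, but it is not stated. Nor do the documents say how items missing by design would be handled.

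**Conclusion.** The point holds for the time-by-staff-type test on the knowledge score. The item counts, the scoring rule and the planned test are all in the documents, and nothing limits the test to common items. The artefact is exactly 0.2 x (change in extra items minus change in shared items) when the groups change equally on shared items.

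Its practical size is uncertain. Under the stated assumptions, the false-positive rate runs from 5% with no gap, through about 6-8% at a 0.25-point gap, to about 11-16% at a 0.5-point gap. The documents give no SD of change, staff split or expected item changes, so these figures are illustrations and not predictions.

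Severity is low. The test is exploratory, the outcome is secondary, and no primary outcome is touched.

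**What to change.** In Protocol 2.5 and the SAP, define the knowledge score for all models that pool staff types, including the time-by-staff-type test, as the mean of the eight items asked of everyone. Report the 10-item mean, or the two extra items, as a separate analysis in clinical staff only. This makes the artefact exactly zero.

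Also state whether the knowledge measure will be factor-analysed. If so, use the eight common items in all staff, or the ten items in clinical staff only. A complete-case analysis of all ten items would drop every non-clinical respondent.

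The cost is a sentence or two in each document and no new data. The downside is that the two clinical-only items leave the pooled score, although they are still collected and reported.

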Step 8: Pilot test. The drug-use stigma-reduction intervention will be delivered in seven HIV CTCs with high client loads located in areas within the three identified municipalities where PWUD congregate or live. These types of CTCs have on average 20 to 25 staff (clinical and non-clinical) who come into direct contact with clients. Staff of all levels will be trained together, which has been shown to have multiple benefits. Training will be on site at the facility and delivered to all relevant staff together in five, 2.5-hour participatory sessions. Timing of the sessions will be negotiated with each facility to ensure minimal disruption to service delivery, as has been done successfully for the HP+ intervention. Training will be delivered by two master trainers from a local community-based organization (Kimara Peers) who have 20 years of delivering HIV stigma-reduction training, including to health workers, and who also run outreach services and a drop-in center for PWUD and a MAT provider, and an addiction specialist. The training team will include people of lived experience of drug use, who will participate as a panel in one of the sessions.

A mixed-methods approach will be used for assessment: pre-post intervention surveys, training observation, and focus group discussions with intervention participants and trainers. Trainers will complete a process rating form at the end of each session focusing on issues of feasibility, coverage of session content, disruptions, issues raised during the session, and level of participant engagement with the material. The training team will maintain attendance rosters for each session, noting when participants leave the room and whether and when they return. The site PI and a member of the field staff will each observe, between them, half of all sessions across the seven facilities, recording observations on the same issues

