2.2 Study population for the pilot study (Inclusion and Exclusion criteria)

The pilot training intervention will be delivered to CTC staff.

The inclusion criteria for CTC staff will be having duties of provision of health services that include having direct contact with clients seeking HIV treatment services, whether they are dedicated CTC staff or shared staff within the wider facility (e.g., lab, guards) and being 18 years or older. The exclusion criteria will be being mentally incompetent or refusal to consent.

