2.3 Study area and clinic selection

The study will be conducted in Dar-es-Salaam, in the Ilala, Kinondoni, and Temeke Municipal Councils. These are the areas the highest concentration of PWUD. The study area has 140 CTCs and three MAT clinics. CTCs and MAT clinics are governed by the municipalities. The intervention will be piloted in seven high-volume HIV clinics in areas with the highest concentration of PWUD. The seven clinics will be selected through a two-step process. Based on existing data on location of where higher concentrations of PWUD live, we will map each CTC's distance from a high drug use area. We will then take the list of all CTCs that would provide close and easy access to the largest concentrations of PWUD (within 5Km) and randomly select the 7 study facilities.

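### The any-of-five cut-off for contact risks a small low-contact group and discards gradation; a 0–5 count from the same items would serve the exploratory contact analysis better.

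*Protocol*

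**What the plan says.** Protocol 2.5 describes a five-item report on how much a respondent "comes into contact with people who use drugs in professional, social, and personal situations". Its two scoring rules are that "agreement with none of the 5 items indicates a low degree of contact" and that "agreement with one or more of the 5 items indicates a high degree of contact". The items themselves are not shown.

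The Protocol abstract (Data analysis) puts level of contact among the covariates of every model. It also names it as an example where interactions with time are planned "to identify possible effect modifiers (e.g., staff type, gender, level of contact with drug users").

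Section 2.2 enrols staff whose duties include "having direct contact with clients seeking HIV treatment services", and it counts shared staff such as laboratory staff and guards. Section 2.3 draws the seven clinics at random from those with "close and easy access to the largest concentrations of PWUD (within 5Km"). Section 1.2, Step 8, adds a feature of the training: "The training team will include people of lived experience of drug use, who will participate as a panel in one of the sessions".

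The SAP collects a contact measure on the ground that contact tends to lower stigma, but its list of control variables does not include it. The SAP then states that "we will individually test each control parameter for an interaction with time".

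**The concern.** The cut-off sits at the very bottom of the scale, and clinic selection favours sites where staff are likely to meet PWUD. If one professional item is true for most respondents, nearly everyone falls in the high group whatever their social or personal contact. The time-by-contact test then compares a handful of people with everyone else. A null result could be read as showing that contact does not matter, when the test could hardly have shown otherwise.

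Timing is a second, conditional issue. Neither document says which wave's contact value enters the models. If an endline value were used, and if the item wording let the training panel count as contact, attending the training could itself move a respondent from low to high.

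**Working it through.** **Inputs.** From Protocol 2.5: low = 0 of 5 items, high = 1 or more. From Protocol 2.4 and the SAP Power Analysis: 131 staff with both surveys, alpha 0.05, d = 0.32. Not in the documents: item wording, the proportion answering true to each item, and the expected split. Those rates are assumed below and varied.

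**1. The plan's own figure.** None is given for the contact split or the interaction. The stated 85% power concerns the overall pre-post change. With 131 pairs and d in SDs of change, a two-sided paired t-test gives 95%. With d in SDs of the raw score, 85% requires a pre-post correlation of about 0.26, which is not stated. This does not bear on the present point; 0.32 serves below only as a yardstick, in SDs of the change score.

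**2. Size of the low group.** Let p1 be the rate for a professional item and po the rate for each of the other four. If items are independent, P(low) = (1 − p1)(1 − po)^4. The standard error of a high-versus-low difference in change, relative to an even split, is 1 / [2√(P(low)(1 − P(low)))].

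| p1 | po | P(low) | n of 131 | SE ratio | Information kept (step 4) |
|---|---|---|---|---|---|
| 0.80 | 0.10 | 0.20 × 0.90^4 = 0.131 | 17 | 1.48 | 42% |
| 0.95 | 0.30 | 0.05 × 0.70^4 = 0.012 | 2 | 4.59 | 6% |
| 0.30 | 0.30 | 0.70^5 = 0.168 | 22 | 1.34 | 43% |
| 0.20 | 0.20 | 0.80^5 = 0.328 | 43 | 1.07 | 61% |

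Positive correlation between items would raise the low share, but never above 1 minus the rate of the most endorsed item. With p1 at 0.80–0.95 that ceiling is 20% down to 5%, or 26 down to 7 of 131.

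**3. Power of the binary interaction.** Treat it as a two-group comparison of change scores, two-sided 0.05, with noncentrality 0.32 / √(1/n_low + 1/n_high).

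- 10% low (13 v 118): 0.32 / 0.292 = 1.10, power 19%. The difference detectable with 80% power is 2.80 × 0.292 = 0.82 SD.
- 5% low (7 v 124): power 13%.
- 20% low (26 v 105): power 31%.
- 30% low (39 v 92): power 38%.
- Even split (66 v 65): 0.32 / 0.175 = 1.83, power 44%. The detectable difference is 0.49 SD.

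These figures ignore clustering in seven clinics and covariates.

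**4. What the cut discards.** If the effect of contact is linear in the count X, the dichotomy keeps a share r² = E(X)² P(low) / [Var(X)(1 − P(low))] of the count's information. First row: E = 1.2, Var = 0.52, so 1.44 × 0.131 / (0.52 × 0.869) = 0.42. Last row: E = 1, Var = 0.80, so 0.328 / (0.80 × 0.672) = 0.61. Even with a third of staff in the low group, about 39% of the information is lost.

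**5. The two documents compared.** The Protocol abstract has both the contact report and a last-month count of drug-using clients treated as covariates. The SAP control list has the client count but not the contact report, so the SAP's interaction rule does not, as written, reach the contact report.

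**The case against.** A reader might infer that almost no low-contact group will remain and that the modifier question cannot be answered. The documents do not support that. Eligibility requires contact with HIV clients, not with PWUD, and takes in guards and laboratory staff. Clinics are chosen by distance, which does not establish that PWUD attend them; the Protocol's own background says stigma keeps them from care. Item wording and rates are unknown, the assumed range runs from about 1% to 33% low, and independence understates the low share if items correlate positively. The SAP also tests the last-month count of drug-using clients against time, so workplace contact has a graded measure already. All of this stands, although that count does not cover social or personal contact.

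A reader might also infer that adjusting for contact will remove part of the training effect. That needs an endline value and item wording that the panel would satisfy; neither is stated. If few people are low at baseline, few can move.

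Finally, this is an exploratory analysis in a single-arm pilot, and even an equal split has only 44% power at 0.32 SD. That limits the severity. It does not defend the cut, which loses information at every split examined.

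**Conclusion.** The point holds as a cheap improvement of minor severity. The cut-off treats one contact as five and, in this setting, risks a low group of about 1–13% (2–17 of 131) under the first set of assumed rates, or 17–33% under the second. If 10% or fewer are low, power for a 0.32 SD difference in change is at most about 19%, and a null interaction would carry little meaning. The loss of gradation does not depend on the low share being tiny: the dichotomy keeps roughly 6–61% of the count's information across the scenarios, given independent items and a linear effect. The unadjusted pre-post comparison is untouched. The mismatch between the Protocol abstract and the SAP control list is plain from the text and rests on no assumption.

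**What to change.** - In Protocol 2.5, score contact as the number of true items (0–5). Enter it as a linear term, both for adjustment and for the time-by-contact interaction.
- Use the baseline value at both waves. This removes any doubt arising from the panel session, whatever the item wording.
- Report the full 0–5 distribution, so that readers can judge what the interaction could have shown.
- Do not substitute a median split. With p1 = 0.80 and po = 0.10, P(0) = 0.13 and P(1) = 0.58, so the median is 1, and a split there can reproduce the present cut of 0 versus 1 or more.
- Reconcile the Protocol abstract with the SAP: either add the contact report to the SAP's control list, so that its interaction rule applies, or remove contact from the abstract's covariates and modifiers.

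The five items are already in the survey, so the cost is wording in 2.5 and the SAP. The downside is an assumption that the effect is linear in the count and that professional, social and personal contact carry equal weight.
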